Evaluating the Efficacy of Lateral Heel Wedges for Osteoarthritis of the Knee

NCT: 02254473 March 1, 2014

Evaluating the Efficacy of Lateral Heel Wedges for Osteoarthritis of the Knee

Principal Investigator: [name]

Significance

Given the prevalence of osteoarthritis of the knee and the general aging trends of the population it is important to develop effective non-operative interventions to reduce pain and improve function in the adult population with osteoarthritis (OA) of the knee. A large body of experimental evidence documents the potential for cartilage regeneration in the osteoarthritic joint under conditions of mechanical unloading of the involved joint. An easily applied, off-the-shelf shoe insert material that, when configured properly, will unload the medial compartment of the knee has been developed. The purpose of this investigation is to document the acceptability and effectiveness (with patient reported measures) of this insert compared to a control insert which does not unload the medial compartment of the knee in a group of patients with significant OA of the medial compartment of the knee in order to develop pilot data to document the effect size, acceptability of the inserts, compliance, feasibility, and power for a future clinical trial. Following communication with NIAMS officials we plan to submit an R34 proposal for this purpose. Multiple clinical trials measuring the impact of shoe inserts on knee OA symptoms report minimal benefit. These trials are conducted in a manner which used: 1. self-reported OA, 2. subjects not presenting for treatment and 3. Not in a stratified population of patients with moderate to severe medial compartment OA. Our study selects for patients with this moderate to severe medial compartment OA who pass the screening test of sufficient MCL laxity to allow correction of the weight bearing axis. Further the material used in these inserts is of a different stiffness which is molded to that of the human heel pad. This clinical trial will likely never be industry funded because of the inexpensive nature of the intervention.

Objectives and Hypothesis

Regularly wearing a 5 degree sloped insole over the course of one year will result in a wider joint space by x-ray in 60% of the subjects, a significant decrease in knee pain, decreased use of over the counter analgesics, and a clinically important 2 point improvement in the Womac pain and stiffness scale.

Methods

We will recruit 80 adults with Kellgren-Lawrence changes between grade 2-4 medial compartment osteoarthritis of the knee from the TRIA Orthopaedic Center in Minneapolis, MN. The subjects will be randomized to a 5 degrees lateral wedge shoe insert or a flat shoe insert of similar properties through a random table generator application which will be coordinated through the TRIA Orthopaedic Center.

Inclusion Criteria:

- Adult patients 30 years or older with symptomatic medial compartment knee osteoarthritis and Grade 2-4 Kellgren-Lawrence radiographic changes presenting for treatment of knee pain.
- Range of motion knee-flexion beyond 100 degrees and not lacking more than 15 degrees of extension.
- Subtalar and forefoot motion permitting foot/ankle eversion with weight bearing.
- Sufficient shoe toe box height to allow space for the insole and therefore comfort and compliance.
- Passive laxity of medial capsule and collateral ligament by knee extension test.

Exclusion Criteria:

- All other forms of knee arthritis other than osteoarthritis.
- Bilateral symptomatic osteoarthritis of the knee.
- Knee Instability- medial pseudo-opening of greater than grade 1 or detectable anterior-posterior instability.
- Less than Grade 2 Kellgren-Lawrence radiographic changes in the medial compartment of the knee.
- Kellgren-Lawrence radiographic changes that are greater than or equal to the medial compartment in either the patellofemoral or lateral compartment.
- Inadequate knee range of motion as demonstrated on exam.
- Balance problems requiring the use of a walker or wheel chair (ambulation with aid).
- Diabetes with peripheral neuropathy.
- History of knee arthroscopy on the index knee within the past three months of study enrollment.
- History of reconstructive (ligamentous etc.) knee surgery within one year of enrollment.
- Intra-articular steroid injection or visco supplementation on the index knee within 1 month of study enrollment.
- Stiff subtalar or forefoot joints as demonstrated on clinical exam.
- Inadequate shoe toe box depth to accommodate the shoe insoles.
- Charcot joint.
- Fixed contracture of the medial capsule and/or collateral ligament as demonstrated on clinical exam.

Rationale for Inclusion:

This group would otherwise be candidates for surgical intervention. Those with end stage osteoarthritic lesion would have biological potential for restoration of the cartilage. They would have range of motion that provided near normal gait and flexion enough to rise out of a chair. The insole fitting would accommodate the candidate's foot anatomy, any pathology and the geometry of their shoe.

Rationale for exclusion:

This criterion removes those conditions that would have potential to add conflicting data to the study and/or produce discomfort for the subject.

Statistical analysis plan:

All analyses will be done using S.A.S. (version 9.2) and two-sided p-values of less than 0.05 will be considered statistically significant. Appropriate descriptive summary statistics (including means and s.d.) and graphs (including histograms, kernel smoothed density plots, error bar plots) will be utilized to summarize Womac pain, stiffness and function in each treatment group at baseline, 6 month visit and 12 month visit. We will consider a linear regression using the generalized estimating equation (gee) approach to estimate the Womac pain, stiffness and function differences between wedge insert and flat insert groups with intention-to-treat principle. We selected gee as the primary approach as it accounts for the potential correlations among repeated measures within subjects. In addition, it has been shown the gee is more efficient compared to the two sample t-test, the paired t-test, the analysis of covariance (including treatment and baseline response as covariates), and is asymptotically equivalent to the analysis of covariance ii (including treatment, baseline response and an interaction between treatment and baseline response as covariates) 40. Missing data will be handled with multiple imputation using S.A.S. proc mi and mianalyze. Secondary outcomes will include clinical and functional outcomes with standardized knee radiographs, a validated University of Minnesota pain and acceptability scale, a medication log in terms of weekly hours of insert usage will be analyzed similarly and the Tegner Activity Scale to document any change in activity level in addition to the function addressed in the other outcomes instruments

Test Intervention:

The Insoles: A commercially available proprietary insole in the form of a slab 10.5 cm wide and 35.5 cm. long will be used. They are available in two geometries and materials. The control insole is blue in color with a thin felt cover to be next to the subject's skin. It is 3 mm level depth side to side and front to back. The material is a proprietary material known commercially as Poron® with a durometer of 25; the average durometer of the human foot is 25-35 depending upon the thickness of the plantar soft tissue and the presence of bone beneath.

The experimental insole is a slab is green in color and made of polyvinyl acetate with a felt layer opposite the patients skin. It has a 5 degree wedge and is 3 mm high on thin side and 10 mm high on the other side. This insole will be fitted with the pattern cut so the outer side of the foot would have the maximum depth of material (the highest side).

Study Procedures:

Patient related: We will recruit 80 subjects presenting for treatment of knee who have primary OA of the knee primarily involving the medial compartment and meet the inclusion criteria. The will be randomized via a random table generated computer program to the wedge inserts or the flat inserts. They will be screened for adequate knee laxity and subtalar motion before enrollment at each site.

Subjects, experimental and control, will complete the Womac based on their current function, have bilateral standing knee radiographs obtained in a standardized fashion and be fit with the inserts and instructed to return in 6 weeks to have new inserts fashioned. The patient contact will be performed by the clinical coordinator. At the 6-week visit, the patients randomized to the wedge insole will have the 5 degrees insoles fit after their 6-week adjustment period with the 2.5 degrees insoles while those in the control group will be fit with new inserts.

At 3, 6, 9 and 12 months, all patients will return for new inserts and to complete secondary radiographs (6 months only) and to turn in their shoe insert acceptability, use logs and medication logs. Patients will be supplied with as many inserts as they need to assure that the shoes they wear on a daily basis are included.

At 1 year, a convenience sample of 5 patients in the wedge (treatment) group and 5 patients in the control group who have had prior knee MRI's within 1 year of institution of the treatment shoe inserts will have knee MRI's repeated to check the quality of medial compartment articular cartilage.

Statistical Analysis

The data analysis will be done in a blinded fashion by our statistician. The Womac and Tegner data will be analyzed with standard statistical approaches and confounding variables of medication use and time of use of the shoe inserts will be analyzed with regression techniques. Knee medial compartment width will be measured by two blinded radiologists.

Subject Instructions: Subjects will be informed they are eligible to be part of a study testing various insoles of differing color, material and shape for their impact on arthritic knee pain and function. They will be instructed on insertion and removal of the insoles including printed material of such instructions. After a 6 week run in period utilizing the 2.5 degree lateral wedge test article in order to adjust to the altered weight bearing axis, the subjects will have a 5 degree wedge test article fashioned in the same manner. They will be instructed to return at 3 month intervals for fitting of new insoles and clinical evaluation. X-rays , medication logs, U of MN pain scale¹, Tegner and Womac will be collected at enrollment, 6 weeks, 3 months, 6 months, 9 months and one year.

Tailoring the Insole:

An exam will be performed ensuring the subjects foot and ankle range of motion.

The existing insoles will be removed from both shoes. This method provides maximum toe box height. It also makes a more uniform insole material bilaterally thereby providing consistency. In both groups the insole will be tailored to the subject's anatomy, pathology, and existing shoe geometry. The subjects will be fitted with the tailored insole that extends from the back of the heel to just beyond the metatarsal head, thereby maximizing room in the toe box. Multiple tailoring may be necessary to achieve comfort. The subjects are instructed on the ease of removing and placing the insole so they can move them shoe to shoe, day to day. The insoles will be replaced every 3 months. The Study Coordinator at the local site will have printed instructions to facilitate and perform the fitting of the test and control inserts based on patient randomization.

Our podiatry consultant will be involved with the training of the research coordinator for patient screening for adequate knee medial laxity and subtalar motion as well as proper fitting of the inserts. He will be the primary contact for questions during the trial related to insert fit. We will hold a one day meeting at TRIA Orthopaedic Center in Minneapolis for the site investigator to review study procedures emphasizing patient screening and consent, procedures for standardizing radiographs, and the technique for application of the shoe inserts and procedures for managing drop out of patients.

Procedures for standardization of subject screening and recruitment, application of test and control inserts; radiographic measure will be done at a one day meeting for the staff at TRIA Orthopaedic Center. The details of the administration of the U of MN pain scale, shoe insert use log, insert acceptability scale, medication log, Tegner and Womac will be reviewed.

With approval from NIAMS officials, we intend to follow this proposal with an R34 submission in order to plan the definitive clinical trial using the data from this proposal to develop a detailed Manual of Operations, calculate the subject numbers we will need to recruit, the estimated number of subjects we might lose to the one year follow-up requirement, the number of additional clinical sites needed to recruit the cohort within a 6 month period, and develop statistical approaches to manage confounding variables such as patient BMI, activity levels, and medical comorbidity.

Table 2:

	Initial visit (Randomization)	6 week	3 month visit	6 month visit	9 month visit	12 month visit
WOMAC, Tegner, and Pain scale	S	S	S	S	S	S
Standing AP bilateral	Р	Х	X	S	Х	Х
Lateral Affected knee	Р	Х	X	S	Х	Х
Medication log	Х	S	S	S	S	S
Shoe insert log	Х	S	S	S	S	S
Clinic visit	Р	S	S	Р	S	Р
MRI						S

P = patient expense; S = study expense; X = not done

Benefits of this intervention and study design:

The subjects have end stage osteoarthritic lesions with potential for cartilage regeneration based upon the literature. Avoidance of surgery is advantageous to the patient. The material properties of the insoles are known. The durometer of the material is known which is relevant to the human plantar surface hardness. The material has an immediate memory to restore shape and depth which is a shorter interval than the human tissue on the plantar surface it is contacting. The fitting method provides the best opportunity for subject comfort and therefore compliance. The removal of the existing insoles removes a variable. The patient instruction during the fitting process; placement, removal and replacement educates them on the means of moving insoles from one shoe to the next. Insoles replacement every three months insures effectiveness of the material properties. The duration of the clinical trial is one year, a time sufficient to be compared to the time interval reported following high tibial osteotomy for cartilage to regenerate in similar lesion²²

Strengths of the proposed intervention:

The method of tailoring the insoles for anatomical and pathological customization should minimize discomfort and increase compliance. The plain film standing x-ray with measured joint space is a clear marker for change. The final MRI is a valid means of measuring cartilage volume and nature. The measurement emphasizes anatomical and pathological variables, thereby removing subjectivity. The single subjective outcome measure will be the Womac. The cost of the insert to the patient would be far less than if a custom insert was constructed into the shoe or any other form of treatment, surgery or otherwise.

C) Research Timeline

	6 months	12 months
Specific Aim 1	Regulatory Paperwork Approval, Study Orientation for staff, and patient enrollment	Patient Follow-up, data analysis, project completion

References

- 2. Bellamy N. Pain assessment in osteoarthritis: experience with the WOMAC osteoarthritis index. Seminars in Arthritis and Rheumatism. 1989;18(4, Supp. 2):14-17. PBS Record: 130

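### The one-year x-ray hypothesis has no one-year film in two of the three places that set the film schedule, and its 60% has no comparator and no matching analysis

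*Combined protocol and SAP*

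**What the plan says.** **Hypothesis.** Objectives and Hypothesis predicts that a 5 degree "insole over the course of one year will result in a wider joint space by x-ray in 60% of the subjects". It gives no rate for the flat insert and no minimum amount of widening.

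**Film schedule.** Three places address it.
- Study Procedures has patients return at 3, 6, 9 and 12 months, among other things "to complete secondary radiographs (6 months only"). A baseline film is also taken.
- Table 2 has both film rows (standing AP bilateral, lateral of the affected knee) at the initial visit and at 6 months. Every other visit, including 12 months, carries the code for not done.
- Subject Instructions says "X-rays , medication logs, U of MN pain scale¹, Tegner and Womac will be collected at enrollment, 6 weeks, 3 months" and continues to the end of follow-up; the full list is "enrollment, 6 weeks, 3 months, 6 months, 9 months and one year".

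**Other one-year imaging.** "At 1 year, a convenience sample of 5 patients in the wedge (treatment) group and 5 patients in the control group" will have a repeat MRI, if they had an earlier one.

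**Analysis.** The Statistical analysis plan specifies a GEE linear regression for WOMAC differences between arms, by intention to treat, with summaries by arm at baseline, 6 and 12 months. On radiographs it says "Secondary outcomes will include clinical and functional outcomes with standardized knee radiographs", and the same sentence goes on to "a medication log in terms of weekly hours of insert usage will be analyzed similarly". The later Statistical Analysis section adds that two blinded radiologists measure medial compartment width.

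**The concern.** A hypothesis stated at one year needs a measurement at one year. Two of the three places that set the film schedule provide none. The timing is central to the plan's own reasoning: Benefits of this intervention and study design defends the one-year duration by the time reported for cartilage to regenerate after osteotomy, and Strengths of the proposed intervention presents joint space on the standing film as a clear sign of change. If the last film is at 6 months, the x-ray part of the hypothesis goes unanswered at the time the plan argues for.

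The second difficulty is the form of the claim. A percentage of wedge wearers with a wider space says nothing about the wedge until it is set against the flat insert. The trial randomises a flat arm that could supply the comparison, but the hypothesis does not use it and the analysis plan does not analyse the percentage.

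**Working it through.** **1. The plan's own figure.** The 60% comes with no derivation, comparator, threshold or power, and the sample size of 80 is not derived from it. There is nothing to reproduce.

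**2. The schedules side by side.**

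| Source | Film dates | Per patient | For 80 patients | Film at 12 months |
|---|---|---|---|---|
| Study Procedures | baseline, 6 months | 2 | 2 × 80 = 160 | no |
| Table 2 | initial visit, 6 months | 2 | 2 × 80 = 160 | no, marked not done |
| Subject Instructions | enrolment, 6 weeks, 3, 6, 9, 12 months | 6 | 6 × 80 = 480 | yes |

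The prose of Study Procedures agrees with Table 2, so a broken table does not explain the conflict.

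**3. Can the hypothesis be evaluated?** Under the first two rows it cannot, because there is no one-year x-ray. Under the third the films exist, but the proportion still has no planned analysis.

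**4. What a 6-month film would reflect.** Study Procedures says wedge patients "will have the 5 degrees insoles fit after their 6-week adjustment period with the 2.5 degrees insoles". Taking 26 and 52 weeks for 6 and 12 months:
- weeks at 5 degrees by the 6-month film: 26 − 6 = 20
- weeks at 5 degrees by one year: 52 − 6 = 46
- ratio: 20/46 = 0.435, about 43%

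**5. What the analysis plan covers.** The secondary-outcomes sentence is garbled, so there are two readings.
- *The WOMAC approach carries over to width.* Then intention to treat, summaries by arm and the baseline, 6-month and 12-month time points carry over with the model. The plan has a comparison of mean width, but its 12-month time point conflicts with Table 2.
- *It does not carry over.* Then no analysis of width is specified.

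On neither reading is the proportion with a wider space analysed.

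**6. Why 60% needs a comparator (illustration only).** Assume that change in width is normal with equal SD in both arms and that *wider* means any increase. The between-arm difference implied by 60% in the wedge arm is z(0.60) − z(flat rate), in SDs of change:

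| Assumed flat rate | Difference |
|---|---|
| 50% | 0.253 − 0 = 0.25 SD |
| 45% | 0.253 + 0.126 = 0.38 SD |
| 40% | 0.253 + 0.253 = 0.51 SD |
| 35% | 0.253 + 0.385 = 0.64 SD |

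The documents give no flat rate, so none of these rows can be preferred. The same 60% fits effects that differ more than twofold.

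**The case against.** **The analysis plan may already cover more than it seems to.** If the secondary outcomes follow the WOMAC approach, width inherits a randomised comparison, intention to treat, summaries by arm and time points. This stands. A reader might infer that the SAP gives no time point for width or ignores the flat arm; the generous reading does not support that. What remains on that reading is narrower: the inherited 12-month time point has no film in Table 2, and the 60% has no analysis.

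**Subject Instructions does provide one-year films.** It does, so the documents do not show that a one-year film will be missing. They show that the plan contradicts itself. That sentence is also loose: it puts medication logs at enrolment, where Table 2 marks them as not done. The 480 figure is therefore weak evidence of an intention to film at every visit. The contradiction does not depend on it.

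**60% is not a decision rule.** Correct. A reader might infer that the trial would be declared positive at 60%, and might then calculate how often chance alone reaches that figure. No passage makes 60% a success criterion, so such a calculation would test a rule the plan does not contain. Likewise, no passage plans a between-arm test on the MRI subsample, so its small size is not an error.

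**This is a pilot, and joint space is secondary.** Both are true. Effectiveness is tied to patient-reported measures. But a pilot meant to document effect size still needs a between-arm estimate at a defined time.

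**A mean difference is not the only repair.** Also true. Comparing the proportion *wider* between arms would keep the stated form, provided *wider* is defined.

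**Conclusion.** The point holds as an internal inconsistency with a lesser gap in the analysis. The hypothesis is set at one year, Study Procedures and Table 2 schedule no one-year film, and Subject Instructions schedules one. If the first two govern, the x-ray hypothesis cannot be evaluated as stated, and the available film reflects about 20 of the 46 weeks at 5 degrees. The one-year MRI in 5 patients per arm does not fill the gap. The 60% has no flat-insert rate and no planned analysis; at most, mean width is compared between arms.

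The schedule finding rests on the text alone. The 20 and 46 weeks assume that the change of insole takes place at week 6. The illustration of what 60% could mean rests on assumed flat rates and normality, and the conclusion does not need it. *The subjects* is read as wedge wearers.

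A reader might infer that the trial's main conclusion is at risk. The documents do not support that: radiographs are a secondary outcome and the WOMAC analysis is untouched. The sponsor should correct this, but it does not undermine the trial.

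**What to change.** 1. Reconcile Study Procedures, Subject Instructions and Table 2 on when films are taken. Which schedule is right is for the sponsor to settle. Then give the hypothesis and the radiographic analysis a time point at which films exist. If there is no one-year film, state the x-ray hypothesis as a 6-month one and describe the MRI subsample as descriptive.
2. State the radiographic result as a randomised wedge-versus-flat comparison with a 95% CI. One sound form is the difference in mean change in medial compartment width, by intention to treat and adjusted for baseline width. If the proportion *wider* is reported, give it for both arms and define it: the threshold, the allowance for measurement error, and the rule when the two radiologists disagree.

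**Cost.** If the 6-month film is used, the change is wording only, using the existing flat arm and planned readings, but the one-year claim is given up. If reconciliation leads to a 12-month film, that is up to 80 further film dates (two views each) at a visit already scheduled, so 160 + 80 = 240 in all. Table 2 charges the initial films to the patient, so the study now pays for 80 film dates. If it also paid for the 12-month films, that would double to 160.

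### The joint-space hypothesis is set at one year, but Table 2 and Study Procedures schedule the only follow-up film at 6 months, while Subject Instructions lists films at every visit

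*Combined protocol and SAP*

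**What the plan says.** Four places in the combined protocol and SAP bear on when the knee is filmed.

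- **Objectives and Hypothesis** sets the time point: "over the course of one year will result in a wider joint space by x-ray in 60% of the subjects".
- **Study Procedures (Patient related)** limits the follow-up film: "At 3, 6, 9 and 12 months, all patients will return for new inserts and to complete secondary radiographs (6 months only").
- **Table 2** has two radiograph rows, standing AP of both knees and lateral of the affected knee. Both show a film at the initial visit (patient expense) and at 6 months (study expense). The 6-week, 3-, 9- and 12-month cells carry an X, which the legend defines as not done.
- **Subject Instructions** opens its list of items collected with "X-rays , medication logs" and gives the collection times as enrollment, 6 weeks, 3, 6 and 9 months, and one year.

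The Statistical analysis plan makes the film secondary: "Secondary outcomes will include clinical and functional outcomes with standardized knee radiographs". It names no time point for the radiographic comparison. The Statistical Analysis section adds: "Knee medial compartment width will be measured by two blinded radiologists". The only other imaging at one year is MRI in "a convenience sample of 5 patients in the wedge (treatment) group and 5 patients in the control group".

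**The concern.** A hypothesis about joint space at one year needs a film at one year. Two of the three places that schedule films say there will be none. The third says there will be one, along with films at four other follow-up visits.

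Staff normally work from the visit table. If they do so here, the first result named in the hypothesis has no data at its stated time, and a film not taken at 12 months cannot be obtained later. The planned multiple imputation would not rescue it, because no patient would have an observed 12-month width from which to impute.

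The 6-month film would then be the only one available to stand in for the one-year result, and it answers a different question. The wedge group starts on a shallower insole, with "the 5 degrees insoles fit after their 6-week adjustment period with the 2.5 degrees insoles", so at 6 months it has had less than half of the 5 degree exposure it will have had by one year. The protocol's own argument in Benefits of this intervention and study design rests on a full year being long enough for cartilage change. A 6-month film does not draw on that argument.

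**Working it through.** The plan gives no power calculation or other figure for the joint-space hypothesis, so there is nothing to reproduce. The check sets the schedules side by side and counts.

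**Inputs**
- 80 patients (Methods).
- Film times as listed in Study Procedures, Table 2 and Subject Instructions.
- 6 weeks on the 2.5 degree insole before the 5 degree one (Study Procedures and Subject Instructions).
- MRI in 5 + 5 patients at one year.
- Assumptions: 6 and 12 months are taken as 26 and 52 weeks from the initial visit. One film set is the standing AP plus the lateral. Counts are before dropout and pool both arms.

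**Films by schedule**

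| | Study Procedures and Table 2 | Subject Instructions |
|---|---|---|
| Follow-up film times per patient | 1 (6 months) | 5 (6 weeks, 3, 6, 9, 12 months) |
| Follow-up sets | 80 × 1 = 80 | 80 × 5 = 400 |
| Total sets with baseline | 80 × 2 = 160 | 80 × 6 = 480 |
| 12-month films | 0 of 80 | 80 of 80 |

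Under Table 2 the study pays for 80 × 1 = 80 of the 160 sets; the baseline set is at patient expense.

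**Exposure to the 5 degree insole when the film is taken**
- At 6 months: 26 − 6 = 20 weeks.
- At 12 months: 52 − 6 = 46 weeks.
- Ratio: 20/46 = 43%.

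Counting all time on any wedge, the ratio is 26/52 = 50%.

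**MRI as a substitute**
- Coverage: (5 + 5)/80 = 12.5%, in a convenience sample of patients who already had a prior MRI. It does not measure joint space by x-ray.

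**Which schedule is likely to be followed**
- Study Procedures and Table 2 agree with each other, and Table 2 is explicit visit by visit.
- The Subject Instructions sentence is a general list. It also puts medication logs at enrollment, where Table 2 marks them as not done, so it is not reliable cell by cell.
- It is nevertheless the only schedule that could test the one-year hypothesis.

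**The case against.** The strongest reply is that the documents divide evenly. Subject Instructions agrees with the one-year hypothesis, and one slip over medication logs does not void its explicit mention of one year. On that view the film schedule merely contradicts itself, and calling it a 6-month schedule is an inference. This stands in part. The documents do not settle which schedule is meant, and the harm arises only if staff follow Study Procedures and Table 2. But relying on Subject Instructions would still require correcting those two places, and would commit the study to 400 follow-up sets instead of 80.

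A second reply concerns weight. This is a pilot whose stated purpose rests on patient-reported measures, radiographs are secondary, and no sample-size figure depends on them. That is right. The WOMAC analysis is untouched: the Statistical analysis plan summarizes "Womac pain, stiffness and function in each treatment group at baseline, 6 month visit and 12 month visit", and Table 2 schedules the WOMAC at 12 months. The point is therefore not critical. Even so, joint space is named first in the hypothesis, and two blinded readers are assigned to measure it.

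A third reply is that 43% measures neither bias nor lost power, and ignores time on the 2.5 degree insole. This is also correct. The figure shows only that the two films follow different exposures; the 50% figure, counting all wedge time, leads to the same conclusion.

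Finally, 6 months may have been a deliberate saving. The documents do not say so. If it was, the hypothesis is what needs to change.

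**Conclusion.** The concern holds. As written, the one-year joint-space hypothesis is untestable under Study Procedures and Table 2 (0 of 80 films at 12 months) and testable only under Subject Instructions (80 of 80). Nothing else in the document resolves the conflict. The 6-month film follows about 20 weeks on the 5 degree insole instead of about 46, and the one-year MRI covers 12.5% of patients.

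The schedule comparison rests on the text alone. The exposure figures assume nominal visit times. This is a matter to correct before films are scheduled. It bears on a secondary outcome and leaves the WOMAC comparison intact.

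**What to change.** Reconcile Objectives and Hypothesis, Study Procedures, Subject Instructions and Table 2 so that the film schedule and the hypothesis share one time point. Keep the baseline film in every case. The sponsor should choose one of the following.

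- **(a) Keep the one-year claim.** Move the study-paid entry in both radiograph rows of Table 2 from 6 to 12 months. Change the restriction in Study Procedures to 12 months only. In Subject Instructions, take X-rays out of the six-visit list and state that they are taken at enrollment and one year.
- **(b) Keep the 6-month film as the only follow-up film.** Restate the joint-space hypothesis and any conclusion as 6-month joint width, and say whether the 60% figure still applies at that time. In Subject Instructions, state films at enrollment and 6 months. Do not use the one-year rationale to support the x-ray result.
- **(c) Keep both films**, naming 12 months as the hypothesis time point.

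**Cost.** Options (a) and (b) are wording and table edits at existing visits. Each keeps 160 sets in total, 80 at study expense.

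The downside of (a) is that patients lost between 6 and 12 months have no follow-up film. The documents give no dropout rate; at assumed losses of 5%, 10% or 20% that is 4, 8 or 16 of 80, to be handled by the planned multiple imputation. The downside of (b) is that the trial makes no one-year joint-space claim.

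Against Table 2, option (c) raises the total from 160 to 80 × 3 = 240 sets: 80 more sets, or 80 × 2 = 160 more views. If the study pays, study-paid sets double from 80 to 160. It also adds 80 × 2 = 160 readings, assuming each radiologist reads each added set once. Taking only the standing AP at 12 months would limit the addition to 80 views. The documents give no budget for this. Against the 480 sets implied by Subject Instructions, all three options are reductions.
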